2.3 Experimental Design

Study Design

This study is a multi-visit (three in total) randomized crossover trial.

Overview

During a single familiarization session, the research team will obtain informed consent, and will describe to participants the purposes and procedures of this study. They will then be exposed to all experimental devices on in a quiet, dimly lit and environmentally controlled room.

Participants will return to the same location for two experimental conditions following these pre-assessment guidelines:

- Fasted (> 12 hours), consuming only water.
- No caffeine consumption 12 hours prior to testing.
- No vigorous exercise 24 hours prior to testing.
- No alcohol consumption 24 hours prior to testing.

Table 1. Study Variables

Type	Measure
Independent (Conditions)	Control (CON): Exposure to MS without PS Sitting-Mental Stress (SMS): Exposure to MS after period of PS
Primary Outcomes	Brain PWV Brachial-femoral PWV
Secondary Outcomes	Executive function Neurovascular coupling Carotid-femoral PWV Augmentation index Femoral-ankle PWV

Experimental Set-Up

[figure not shown]

Figure 1. Experimental setup for to assess full body cardiovascular health. Each experimental device responsible for collecting data is shown in this picture and close ups.

Familiarization

Participants will be familiarized with all experimental procedures and then given the opportunity to ask any questions prior to providing written consents. Subjects will be brought to an upright, seated position using an Armedica AM353 Hi-lo Treatment Table (Tiger Medical, TIGER#TM83695) with feet flat on the ground with approximately 90 degrees of knee flexion. If feet cannot touch the ground, a platform will be used. The angle of recline of the chair will be measured, as well as the distance from the bottom of the chair to the ground to ensure equivalent chair placement for the second visit.

Experimental Visits

Refer to both *Table 1* and *Figure 1* for a breakdown of when experimental measures will be taken through both visits.

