Participants will arrive to the Applied Physiology Laboratory (APL) between 6:00 and 10:00 AM fasted (for Visit 3: 2-5 days following the Visit 2). Participants will be fasted and refrain from caffeine intake for at least 12 hours, and alcohol and strenuous physical activity for at least 24 hours prior to arrival. Upon arrival, height and weight will be recorded followed by 10 minutes of quiet rest in the supine position (white solid boxes in **Figure 1**). During these 10 minutes, the subject will be fitted with a NIRS probe on the prefrontal cortex and medial gastrocnemius. The NIBP, TCD, and VICORDER® devices will also be affixed to the participant during this time period during this time. Sitting periods (solid gray boxes in **Figure 1**) will begin for both conditions once all devices are attached to the participant, the subject is shifted to an upright seated position, and at least 10min of supine rest has been recorded. During the CON visit, subjects will undergo a brief 20min sitting period. For the SMS condition, subjects will be asked to sit still and quietly for 2 hours while watching a non-stimulating documentary. Each condition will receive the MS (black boxes in **Figure 1**) at the conclusion of the sitting periods in both CON and SMS. After exposure to the MS in both conditions, data collection procedures for this protocol will be completed for VICORDER® immediately after the MS and every 5 minutes for 25 minutes (See **Figure 1** for visual details on how and when data is being collected). Brain BF will be assessed by US 20 minutes post-completion of the MAT. Finally, a battery of cognitive tests (Verbal Fluency Test and Trails A+B tests) will be administered to the participant (boxes with diagonal shades in **Figure 1**).

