2.4 Experimental Procedures

[figure not shown]

Figure 2. A visualization of the experimental protocol. Maintenance of external validity for this study will require exposure of the MS to be time-matched between both experimental conditions. The use of accelerometry will allow investigators to observe physical activity and sleep patterns to ensure uniformity in pre-assessment behaviors. All time points are expressed relative to the time of completion of the mental stressor. **Abbreviations:** BF, blood flow; PWV/A, Pulse wave velocity & analysis; (1), collection of PWV/A for the primary outcome, bfPWV/A will be collected at this time point only; (3) collection of PWV/A for bfPWV, cfPWV, and faPWV; PA, Physical activity; t, time; NIRS, Near-infrared spectroscopy; NIBP, Non-invasive blood pressure; TCD, Transcranial Doppler.

Protocol 1: Mental Arithmetic Test

Test Structure					Application																																																																																																																																																																																																		

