2.5 Measurements

Table 2. Summarization of measures used for the protocol, “The Combined Effects of Prolonged Sitting and Mental Stress on Vascular and Cerebrovascular Function in Middle-Aged Adults”. Each experimental variable is listed under the “Outcomes” column with its designation as either a primary, secondary, or mechanistic measure listed under the “Role Classification” column. The “Device” column names the equipment used to collect the data. **Abbreviations:** TCD, Transcranial Doppler; CON, Control condition; SMS, Sitting mental stress condition; VFT, Verbal fluency test; TMT, Trail making test; NIRS, Near-infrared spectroscopy; cwNIRS-SRS, Continuous-wave near-infrared spectroscopy. Minute values are expressed relative to the administration of the MAT.

Outcomes	Device	Unit	Time Period (min)			Role Classification
			Condition	Time Periods (min)	Measurements Taken	
Brain Pulse Wave Velocity	TCD	meters per second (m/s)	CON	Continuous	1	Primary
			SMS	Continuous	1	
Brachial-femoral Pulse Wave Velocity (PWV)	VICORDER®	meters per second (m/s)	CON	-5, 0, 5, 10, 15, 20, 25	7	Primary
			SMS	-115, -15, 0, 5, 10, 15, 20, 25	8	
Executive Function	VFT/ TMT	Cognitive performance: measured in seconds (s)	CON	25	1	Secondary
			SMS	25	1	
Neurovascular Coupling	NIRS/ TCD	Unitless: relationship between local neural activity and subsequent changes in cerebral blood flow. [CITE]	CON	Continuous	1	Secondary
			SMS	Continuous	1	
Augmentation Index (Aix)	VICORDER®	Percentage. It is defined as the difference between the second and first systolic peaks (P2-P1) expressed as a percentage of the pulse pressure ^{24,25}	CON	-5, 0, 5, 10, 15, 20, 25	7	Secondary
			SMS	-115, -15 0, 5, 10, 15, 20, 25	8	
Carotid-femoral PWV	VICORDER®	meters per second (m/s)	CON	-5, 25	2	Secondary
			SMS	-115, -15, 25	3	
Central Blood Pressures (CBP)	VICORDER®	Millimeters of Mercury (mmHg)	CON	-5, 0, 5, 10, 15, 20, 25	7	Secondary
			SMS	-115, -15 0, 5, 10, 15, 20, 25	8	
Femoral-ankle PWV	VICORDER®	meters per second (m/s)	CON	-5, 25	2	Secondary
			SMS	-115, -15, 25	3	
Physical Activity	ActiGraph	Minutes. Activity data will be classified as either "Light", "Moderate", or "Vigorous".	CON	Continuous	1	Mechanistic
			SMS	Continuous	1	
Sleep Duration	ActiGraph	Minutes.	CON	Continuous	1	Mechanistic
			SMS	Continuous	1	
Cerebral Perfusion	cwNIRS-SRS	Relative changes in total hemoglobin concentration (tHb). Expressed as a percentage.	CON	Continuous	1	Mechanistic
			SMS	Continuous	1	

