Brain PWV and Middle cerebral artery velocity (MCAv) will be measured using continuous bilateral TCD (ST3, Spencer Technologies). MCAv accounts for 70-80% of the brain's total perfusion²⁵. The data will be acquired continuously (50 Hz) using an analog-to digital convertor (PowerLab 30, ADInstruments).

DEVICE 3: Non-Invasive Blood Pressure (NIBP)

The PowerLab data acquisition system (PowerLab 30 series, ADInstruments, CO, USA) will be used to simultaneously acquire signals from each device and from ECG. A standard Lead II ECG will be recorded from three electrodes placed on the right and left shoulders, and just below the left rib. The signals from the ECG and two test devices will be sampled a frequency was 1000 Hz, providing a temporal resolution of 1ms.

DEVICE 4: Doppler Ultrasound

A commercial ultrasound device equipped with 11-3 MHz linear array probe will be used. Experimenters will assess blood flow in three cerebral arteries: common carotid, internal carotid, and vertebral.

DEVICE 5: Continuous Wave Near-Infrared Spectroscopy with Spatially Resolved Spectroscopy (cwNIRS-SRS or NIRS)

A continuous, non-invasive system to measure cerebral perfusion. The near-infrared spectroscopy probe used in this protocol emits a single frequency of light (cwNIRS) to monitor relative change in total hemoglobin. Using the spatially-resolved spectroscopy (SRS) technique, cwNIRS can estimate absolute measures of perfusion (e.g. total hemoglobin, tissue saturation index). The cwNIRS-SRS device will be positions on the forehead, approximately 3cm to the right of the center, directly over the eyebrow. An additional probe will be placed over the medial gastrocnemius to observe venous pooling of blood in the lower-limbs. The location of both probes will be marked to ensure identical placement for the next experimental session. The device will be covered with a dark opaque cloth to prevent signal contamination by ambient light as per manufacturer recommendations.

DEVICE 6: ActiGraph

An ActiGraph accelerometer will be distributed to the research participant at the conclusion of the familiarization session along with a sleep journal packet. The subject will be asked to record on the timeline when he/she began to sleep and awaken each day until the conclusion of his/her participation in this study. The device will be worn on the individual's non-dominant wrist according to manufacturer guidelines. The data collected from this device will be used for one purpose:

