- Validate the subject's compliance with pre-testing behavioral restrictions for the purpose of internal validity:
 - Waking up at similar times on the mornings of both experimental session

DEVICES 7 & 8: Data Acquisition (PowerLab) and Data Processing (LabChart)

For the TCD and NIBP, devices, data acquisition and processing will be automated using the accompanying software.

[figure not shown]
For the two test devices, the PowerLab data acquisition system (PowerLab 30 series, ADInstruments, CO, USA) will be used to simultaneously acquire signals from each device and from ECG.

LabChart 8 (ADInstruments) will record and process the data acquired using PowerLab. The ECG signal does not require any post-processing, the software filters ensure a distinct R peak. The foot of the pressure waveforms from the NIBP and PPG devices will be identified using a standard second derivative function. Offline, a custom macro will identify the peak of the R wave and the peak of the second derivative of each pressure waveform, then calculate the time between said peaks.

Cognitive Measurement 1: Trails A+B Tests

Test Structure & Application

The Trail-Making Test – Part A, the circles are numbered 1 – 25, and the subject will draw lines to connect the numbers in ascending order. Part B presents numbers and letters placed in a semi-random fixed order, in such a manner to avoid overlapping lines being drawn. The subject will connect 25 encircled numbers and letters in numerical and alphabetical order, alternating between the numbers and letters. For example, the first number “1” is followed by the first letter “A” followed by the second number “2” then second letter “B” and so on²³ Results for both TMT A and B will be reported in seconds.

Cognitive Measurement 2: Verbal Fluency Task

Test Structure		Application	
Tests of verbal fluency evaluate an individual's ability to retrieve specific information within restricted search parameters ²⁴ . The two subtests are (1) semantic fluency, and (2) phonemic fluency. The total number from each test will be summed and equate to the subjects' cognitive performance.		Verbal Fluency Test	
Phonemic fluency		Rapid generation of words beginning with a specific letter. Typically, F, A, and S are used as stimulus letters.	Instructions
Semantic fluency		Rapid generation of words from within a semantic category. "Animal names" and "supermarket items" are commonly used.	

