Example Set-up	  
SLEEP DIARY
 
Each line represents 24 hours from midnight one day to midnight the following day
 
Please enter on each line when you begin trying to sleep (BGN) and finish trying to sleep (FSH) for any sleep 10 minutes or longer. Also record if or when you take it off (OFF) and back on again (ON).
 
This line gives you an example on how to fill out the sleep log. Carry sleep time over to the next line if necessary.
 
Example: 000 020 040 060 080 1000 120 140 160 180 200 220 240 00:15 BGN 06:15 FSH 10:00-10:15 OFF 23:00 BGN
 
Date: / / 000 020 040 060 080 1000 120 140 160 180 200 220 240
 
Date: / / 000 020 040 060 080 1000 120 140 160 180 200 220 240
 
Date: / / 000 020 040 060 080 1000 120 140 160 180 200 220 240
 
Date: / / 000 020 040 060 080 1000 120 140 160 180 200 220 240
	
 Device is worn on the non-dominant wrist To maintain internal validity subjects will be asked to complete a sleep journal that details when the ActiGraph device is being worn, when the participant goes to sleep, and when he/she awakens. This information will only be used to validate the adherence of the participant to pre-test behaviors: Waking up at relatively the same time of the morning, no vigorous exercise 24hr prior

Raw Data		
 Upper image: 24 hour observation of counts of physical activity and ambient light throughout several days Lower image: More detailed view of physical activity counts.
Data Analysis		
 Trained researchers will use the returned sleep journal to set cut points for the beginning and end of sleep periods of the research participant This process allows more accurate reports of ambient physical activity before and during experimental sessions
Data Reduction		
 Data can be reduced on an hourly or daily basis Accelerometry data separates daily ambulation into different categories: sedentary, light, moderate, and vigorous

DEVICES 7 & 8: Data Acquisition (PowerLab) and Data Processing (LabChart)

Device		
 Company: ADInstruments Model: PowerLab 8/35 Location: Sydney, Australia Device will work in conjunction with LabChart software and NIBP cuff
--------	---	---

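### Sitting between waking and arrival is unrestricted, and the accelerometer data that could show it have no planned check, although the CON morning has about 110 extra unsupervised minutes

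*Combined protocol and SAP*

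**What the plan says.** **The exposure.** Under section 2.3, in SMS "subjects will be asked to sit still and quietly for 2 hours while watching a non-stimulating documentary"; for the control, "During the CON visit, subjects will undergo a brief 20min sitting period". The CON timeline in section 2.6 shows 10 min of sitting before the stressor (-15 to -5), not 20.

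**Timing.** The Figure 2 legend in section 2.4 says "Maintenance of external validity for this study will require exposure of the MS to be time-matched between both experimental conditions". Both timelines in section 2.6 put the arithmetic test at -5 to 0, with 10:40 AM as the example. First contact is at -30 min in CON (10:15 AM) and -140 min in SMS (8:25 AM).

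**Behaviour before the visit.** The section 2.3 list covers fasting, caffeine, alcohol and exercise ("No vigorous exercise 24 hours prior to testing"). It has no item on sitting, desk work or travel.

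**The accelerometer.** It is attached at familiarization. Section 2.5 states "The data collected from this device will be used for one purpose" and gives one item: "Waking up at similar times on the mornings of both experimental session". Section 3 adds the vigorous-exercise rule and says "Accelerometry data separates daily ambulation into different categories: sedentary, light, moderate, and vigorous". In Table 2, "Activity data will be classified as either" light, moderate or vigorous; sedentary is not listed. The Figure 2 legend gives the device a wider role, uniform behaviour before assessment, without a measure, threshold or action. Section 4.2 contains no term or check for sedentary time before arrival.

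**The concern.** The objective in section 1.1 depends on the control visit being free of a recent bout of prolonged sitting. The plan controls this only from the moment the participant enters the laboratory. Because the stressor is fixed in time and the CON visit is short, the CON participant is left alone for longer on a morning meant to be otherwise alike.

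Sitting is the likely use of that time in this population. Section 1 describes sedentary behaviour as common through work, technology and vehicles, and section 8.1 recruits working people, partly through workplaces. A CON participant who spends the window at a desk or in a car receives some of the factor under test before any physiological recording starts. The CON-SMS difference would then underestimate the effect of sitting, and nothing in the planned output would show it.

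**Working it through.** **1. Length of the extra window.** From section 2.6: -30 - (-140) = 110 min. The example clock times agree: 8:25 to 10:15 AM is 110 min. With waking time also matched, these are 110 additional waking minutes outside the laboratory on the CON morning. The 10:15 AM example lies outside the 6:00 to 10:00 AM arrival window of section 2.3, but the 110 min follow from the relative timelines and the time-matching, not from that clock time.

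**2. Comparison with the intended contrast.** Supervised sitting before the stressor is 120 min in SMS (-125 to -5). In CON it is 20 min (section 2.3) or 10 min (section 2.6). The contrast is 120 - 20 = 100 min or 120 - 10 = 110 min. The unsupervised window is about as long as the whole contrast.

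**3. Would the CON data reveal it?** Continuous recording in CON starts at -15 min, ultrasound and VICORDER measures fall between -15 and -5, and Table 2 gives the first bfPWV as -5. All come after arrival, so carry-in cannot be seen as a change within the CON visit.

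**4. The plan's own sample size.** Section 4.6 gives a change of 1 m/s, an error of 1.25 m/s, type 1 and type 2 error of 5% each, and about 18 participants. Taking 1.25 as the SD of the paired difference and a one-sided 5% level:

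n = [1.25 × (1.645 + 1.645) / 1]² = 16.9, so 17; the t-based figure is 19. The stated 18 is reproduced within rounding of method.

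**5. Illustration of dilution.** Suppose the effect is proportional to the sitting contrast and CON participants receive an effective fraction f of the extra exposure. The expected difference is 1 × (1 - f) m/s, and power comes from the noncentral t with noncentrality (1 - f)√n / 1.25. At the planned n = 20:

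| f | Effective minutes of 110 | Difference (m/s) | Power, one-sided 5% | Power, two-sided 5% |
|---|---|---|---|---|
| 0 | 0 | 1.00 | 0.96 | 0.92 |
| 0.25 | 27.5 | 0.75 | 0.83 | 0.72 |
| 0.50 | 55 | 0.50 | 0.53 | 0.40 |

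An all-or-nothing version lets a share p of participants lose the contrast completely: mean 1 - p, SD either 1.25 or √(1.25² + p(1 - p)), two-sided 5%, n = 20. Power is 0.84 to 0.86 for p = 10%, 0.73 to 0.77 for 20% and 0.61 to 0.66 for 30%.

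The values of f and p are assumptions with no source in the documents. The 1 m/s and 1.25 m/s relate to aortic (central) PWV, while the primary outcomes are brain and brachial-femoral PWV. The planned analysis is a mixed model, not a paired t-test. The table shows direction and sensitivity; it is not an estimate of the loss.

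**The case against.** Four arguments have force.

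*Sedentary time is in fact recorded.* A reader of section 2.5 and Table 2 might infer that sitting before arrival goes unmeasured. The documents do not support that: the device is issued before both visits, and section 3 lists a sedentary category and speaks of activity before sessions. What is missing is a planned use. The legend of Figure 2 and the remark in section 4.2 that mechanistic outcomes help to rule out extraneous covariates are too general to supply one.

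*Everyday sitting is not the SMS exposure.* It is tempting to say that such a control has had nearly the full exposure. But SMS is still, quiet, upright sitting that runs straight into the stressor. A CON participant must travel, be weighed and measured, and lie supine for 10 min first. Section 1 names pooling in the legs as the first disturbance, and this sequence interrupts it. Full carry-over is unsupported; so is zero carry-over.

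*A null result would still carry information.* Section 4.2 plans within-condition comparisons, and the SMS change in bfPWV from -115 to -15 does not use CON. That stands as a check on whether sitting had an effect. It does not replace the CON-SMS comparison of the response to stress, which is the trial's question.

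*Sitting before the SMS visit would offset some of the loss.* True, but that window is 110 min shorter.

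**Conclusion.** The concern holds as a gap in exposure control with a predictable direction: toward no difference. Its firm parts are the 110-min window, its similarity to the 100 to 110 min contrast, the absence of any sitting rule, and the absence of a planned check on data that will exist. These rest on the stressor and waking times being matched as stated.

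The size of the dilution is not known. It depends on how many participants sit in the window and how much of the effect survives to the first seated measurement. The documents settle neither, so the power figures must not be read as a forecast, nor the point as showing that a null result would be uninterpretable. This is a low-cost improvement that protects the trial's own question, not a flaw that invalidates the design.

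**What to change.** 1. Add to the section 2.3 pre-assessment guidelines an instruction to avoid prolonged uninterrupted sitting between waking and arrival, worded identically for both experimental mornings. An instruction for CON alone would create a new difference between visits. Say whether a breach falls under the rescheduling and withdrawal rule in section 6.4.
2. Add sedentary to the ActiGraph row of Table 2, and reconcile section 2.5 with the Figure 2 legend and section 3 on what the device is for. Reconcile the 20-min and 10-min CON sitting periods as well.
3. Derive sedentary minutes and the longest sedentary bout from waking to arrival for each visit, and report them by condition as an exposure check.
4. Do not adjust the primary model for these minutes. With waking times matched, the CON window is longer by design, so the minutes are tied to condition; with about 20 participants, adjustment could remove part of the contrast itself. Any sensitivity analysis that excludes CON visits should use a bout length fixed before the data are seen.

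Cost: one instruction line, two derived variables from data already collected, and a minor burden on participants. A wrist device classifies sitting imperfectly, and any exclusion analysis would have fewer pairs, so these results should remain supportive.

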2.1 Participants

We will recruit 20 adult (35-59 y) male and female participants. A healthy population sample will be recruited to mitigate the risk of age- or disease-related influences on the study outcomes.

Inclusion Criteria

- Male or female participants will be between the ages of 35-59 years old.

Exclusion Criteria

- Any known cardio-metabolic disorders
- Taking medications known to affect cardiovascular function
- Report drug or alcohol abuse
- Report cigarette smoking
- Pregnant women

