2.2 Allocation to Treatment Groups and Blinding

The randomization procedure will be performed by a research assistant. Participants will be randomized into either CON or SMS intervention for the first visit. This will be done during the familiarization session using an online randomization software (www.randomizer.org).

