11.3	7814																																																																																																																																																																																																						
15.0	7807																																																																																																																																																																																																						
18.8	7800																																																																																																																																																																																																						
22.5	7793																																																																																																																																																																																																						

 Test duration: Approximately 5min Participant is in seated upright position At the beginning of the test, the researcher will call out a four digit number and ask the participant to subtract either 7 or 13 Correct responses will not be recorded as an outcome for this study 																																																																																																																																																																																																							

The MS used for this protocol is the Mental Arithmetic Test (MAT), a commonly used exam to impose a small psychological stimulus on the participant. This test will approximately last for five minutes. The researcher will call out a four-digit number and ask the participant to subtract either seven or 13. Correct responses will not be recorded as an outcome for this study. During this test a metronome will play at a pre-set tempo. The subjects will be required to conduct continuous subtraction with the tempo to the best of their ability. Every minute, a new four digit number will be called out and the participant must subtract the seven or 13 from the number.

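### The plan specifies no alternate test versions, practice run, balanced order or visit term, so practice gained between visits 2-5 days apart can enter the SMS-CON comparison of executive function

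*Combined protocol and SAP*

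**What the plan says.** - **Design.** Section 2.3: "This study is a multi-visit (three in total) randomized crossover trial". The second experimental visit (Visit 3) falls "2-5 days following the Visit 2". Section 2.1: "We will recruit 20 adult (35-59 y) male and female participants".
- **Order.** Section 2.2: "Participants will be randomized into either CON or SMS intervention for the first visit", using online software. No blocking or equal split is stated.
- **Stressor.** Section 2.4 prints one arithmetic table with fixed starting numbers, subtrahends and tempos: 4568 minus 7 at tempo 12, 9149 minus 13 at tempo 14, 7835 minus 7 at tempo 16. The text adds: "Every minute, a new four digit number will be called out". Correct answers are not kept as an outcome.
- **Trails.** Section 2.5, Cognitive Measurement 1: "Part B presents numbers and letters placed in a semi-random fixed order". No alternate form is mentioned.
- **Verbal fluency.** Section 2.5, Cognitive Measurement 2: "Typically, F, A, and S are used as stimulus letters". Categories are likewise given as common examples, and nothing is tied to a visit.
- **Familiarization.** The timetable in section 2.6 covers consent, discussion, 20 minutes of device attachment, and scheduling. It lists no trial run of the arithmetic, Trails or fluency tasks.
- **Scoring.** Table 3 takes a single score per cognitive test per visit. Table 4 marks executive function as not measured at Baseline or Post-PS.
- **Model.** Section 4.2 names time within condition and condition at matching times. It names no visit, sequence or carry-over term.

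**The concern.** Timed tasks such as Trails and verbal fluency are open to practice effects, most of all when the same items come back within days. Executive function is a secondary outcome and has no within-visit baseline to absorb a visit-to-visit gain. The CON and SMS scores are compared directly, so a gain at the second experimental visit is credited to whichever condition more participants happened to have second.

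The arithmetic test is the stressor in both conditions, so familiarity with its items could also soften the stress response at the second visit. Because correct answers are not recorded as an outcome, task scores cannot show whether that happened. Heart rate and blood pressure would be indirect checks only.

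**Working it through.** The plan gives no figure for practice or for executive function. Its one design figure, about eighteen participants in section 4.6, concerns PWV. Taking 1.25 m/s as the SD of the difference, one-sided 5% and 95% power, it reproduces as ((1.645 + 1.645) x 1.25 / 1)² = 16.9, or 19 with the noncentral t. It plays no part below.

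**Inputs.** N = 20 (section 2.1); two experimental visits with randomised order (sections 2.2 and 2.3); one score per visit (Tables 3 and 4); model terms from section 4.2. Let n1 be the number having CON first and n2 the number having SMS first. L is the change in score at the second experimental visit due to practice. It is an assumption with no value in the documents, so results are per unit of L. For Trails, in seconds, improvement makes L negative.

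**1. Same gain in both orders, no visit term.** The SMS minus CON difference is shifted by +L in the CON-first group and by -L in the SMS-first group.

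Bias = (n1 x L - n2 x L)/N = L x (n1-n2)/N

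| Split (CON first : SMS first) | Without visit term | With visit term |
|---|---|---|
| 10:10 | 0 | 0 |
| 12:8 | (12-8)/20 = 0.20L | 0 |
| 14:6 | (14-6)/20 = 0.40L | 0 |

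Noise-free least-squares fits with participant effects gave the same values.

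**2. How likely is an uneven split?** Assume unblocked randomisation of 20 with probability one half.

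- P(10:10) = 184,756/1,048,576 = 0.18
- P(12:8 or more uneven, either direction) = 1 - (184,756 + 2 x 167,960)/1,048,576 = 0.50
- Mean of |n1-n2|/N = 0.176, so the expected absolute bias is about 0.18 of the size of L

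**3. Noise at an equal split.** Without a visit term the +L and -L shifts stay in the paired differences. They add variance L² x [1 - ((n1-n2)/N)²], which is L² at 10:10. The estimate is unbiased there but less precise than it need be. A visit term removes this at the cost of one residual degree of freedom (19 to 18 for 20 paired differences).

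**4. Gain that depends on the first condition.** Let the gain be L_C after CON and L_S after SMS. A model with a visit term averages the two order groups equally.

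Bias = (L_C - L_S)/2

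For illustration, L_C = 1.0 and L_S = 0.5 give (1.0 - 0.5)/2 = 0.25 at 10:10, 12:8 and 14:6 alike. Without a visit term, 12:8 gives (12 x 1.0 - 8 x 0.5)/20 = 0.40, and 14:6 gives (14 x 1.0 - 6 x 0.5)/20 = 0.55. Neither a visit term nor balanced order removes this part. It can only be made smaller by reducing the learning itself.

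**The case against.** **Repetition is not stated.** A reader might infer that participants certainly receive identical items twice. The documents do not say so. The fixed order describes how a Trails form is laid out, the fluency letters and categories are offered as usual choices, and section 7.1 allows that procedure manuals may be needed. This stands for the cognitive tests: the defect is that versions are unspecified. It stands less well for the stressor, because only one script is printed and section 9.3 requires conduct exactly as the protocol describes.

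**Familiarization may include practice.** Section 2.3 says participants are made familiar with every experimental procedure. That could cover practice, but no trial run is described and the section 2.6 timetable leaves no time for one. The two sections need to be reconciled.

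**A visit term deals with ordinary practice.** Correct, as step 1 shows. A reader might infer that practice bias is beyond any model. Only the condition-dependent part is, and the documents hold no evidence that learning differs by order. But section 4.2 names no visit term, so even the removable part is left in.

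**Loss of power.** A reader might also infer that a weaker second stressor shrinks the SMS-CON effect on PWV and so costs power. The documents do not support a figure. They give no size for such weakening. Part of the contrast may already be present after sitting, before the stressor. A drop common to both conditions would not shrink a balanced contrast.

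**Scale.** Executive function is secondary and the study is labelled pilot testing. That limits the weight of the point but does not remove it, given the small cost of the remedy.

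**Conclusion.** The point holds as a gap in specification, and closing it is a cheap improvement. As written, participants may repeat the same items within days, and neither the allocation nor the model protects the executive-function comparison. A common gain L biases SMS minus CON by 0.20L at 12:8 and 0.40L at 14:6, and adds variance L² at 10:10. The 0.50 chance of 12:8 or worse assumes unblocked randomisation of 20 completers; section 2.2 neither confirms nor rules that out. A gain that differs by first condition leaves half the difference in place whatever the model. Both L and that difference are unknown, so the point supports these formulas but no statement in seconds or in power. It does not show that the primary PWV outcomes are biased.

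**What to change.** 1. Prepare a second arithmetic script with the same subtrahends and tempos but new starting numbers, a second Trails layout, and a second set of fluency letters and categories. If alternate versions are already intended, state this in sections 2.4 and 2.5.
2. Assign versions balanced over condition and order. Two orders by two version sequences make four cells, or five participants each at N = 20. Blocked allocation to these cells also gives a 10:10 order split.
3. Run one unscored practice of Trails and verbal fluency at familiarization, and bring sections 2.3 and 2.6 into line.
4. Add a visit term to the mixed model in section 4.2.

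The cost is a few hours of preparation and a slightly longer familiarization session, since its 20-minute slot is already given to attaching devices. Versions may differ a little in difficulty; balanced assignment limits the effect on the condition comparison. New starting numbers address only learning of the particular items, not general ease with timed subtraction.
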